8.3.7. Medical Device Incidents (Including Malfunctions)

Medical devices are being provided for use in this study for the purposes of electroporation. In order to fulfill regulatory reporting obligations worldwide, the investigator is responsible for the detection and documentation of events meeting the definitions of incident or malfunction that occur during the study with such devices.

The definition of a Medical Device Incident can be found in Appendix 6.

NOTE: Incidents fulfilling the definition of an AE/SAE will also follow the processes outlined in Section 8.3.3 and Appendix 3 of the protocol.

8.3.7.1. Time Period for Detecting Medical Device Incidents

- Medical device incidents or malfunctions of the device that result in an incident will be detected, documented, and reported during all periods of the study in which the medical device is used.
- If the investigator learns of any incident at any time after a subject has been discharged from the study, and such incident is considered reasonably related to a medical device provided for the study, the investigator will promptly notify the Sponsor-investigator who will notify the study supporter.

The method of documenting Medical Device Incidents is provided in Appendix 6.

8.3.7.2. Follow-up of Medical Device Incidents

- All medical device incidents involving an AE will be followed and reported in the same manner as other AEs (see Section 8.3.3). This applies to all subjects, including those who discontinue study intervention.
- The investigator is responsible for ensuring that follow-up includes any supplemental investigations as indicated to elucidate the nature and/or causality of the incident.
- New or updated information will be recorded on the originally completed form with all changes signed and dated by the investigator.

8.3.7.3. Prompt Reporting of Medical Device Incidents to Study Supporter

- Medical device incidents will be reported to the Sponsor via email within 24 hours after the investigator determines that the event meets the protocol definition of a medical device incident.
- The same individual will be the contact for the receipt of medical device reports and SAE.

8.3.7.4. Regulatory Reporting Requirements for Medical Device Incidents

- The investigator will promptly report all incidents occurring with any medical device provided for use in the study in order for the Sponsor to fulfill the legal responsibility to notify appropriate regulatory authorities and other entities about certain safety information relating to medical devices being used in clinical studies.

- The investigator, or responsible person according to local requirements (eg, the head of the medical institution), will comply with the applicable local regulatory requirements relating to the reporting of incidents to the IRB/IEC.

8.4. Biomarkers

- Collection of samples for other biomarker research is also part of this study. Tumor biopsies (fixed and fresh) as well as blood and fecal samples will be collected as specified in SoA and Appendix 5 (Section 10.5).
- The main objective of the Immune Monitoring is to characterize the tumor microenvironment and assess the immune phenotype and function pre- and post-study intervention (tavo-EP in combination with nivolumab) prior to as well as post-surgery.
- Samples may be stored according to local regulations following the last subject's last visit for the study at a facility selected by the Sponsor to enable further analysis.

9. STATISTICAL CONSIDERATIONS

9.1. Statistical Hypotheses

This is a Phase 2 single-agent, open-label study. The primary endpoint of this study is the complete pCR at definitive surgery. It is anticipated that combination regimen will improve the pCR from an estimated 10% to 30%.

9.2. Sample Size Determination

The statistical power calculations are based on the Simon 2-stage minimax design ([Simon, 1989](#)). A total of 33 eligible subjects will be enrolled into this study in a 2-stage design. In the first stage, up to 22 subjects can be accrued. If there are ≤ 2 responses in these 22 patients, the study will be stopped. Otherwise if ≥ 3 responses are observed, the study will proceed to Stage 2, in which an additional 11 subjects will be accrued for a total of 33 subjects. If 7 or more responses are observed in 33 subjects, the conclusion will be that the therapy is worthy of further investigation. When the true response rate of 30% (alternative hypothesis) is tested against the null hypothesis response rate of 10%, this design yields a Type I error rate of 0.05 and power of 90%.

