Definitive Surgery Phase: Surgery may be scheduled about 2-4 weeks after the last dose of nivolumab following radiologic and clinical assessment at that point. Pathologic response will be determined by institutional pathologist. Under certain circumstances, the definitive surgery may be delayed and done after completion of additional cycles of neoadjuvant therapy if decided by the treating physician investigators (surgeon and medical oncologist) to be in the best interest of the patient (or can be done earlier if study intervention(s) was discontinued due to AEs or other reasons).

Adjuvant Phase: Adjuvant therapy with nivolumab monotherapy will begin approximately 2-4 weeks following definitive surgery, but can be later as clinically indicated to allow medical clearance for systemic therapy; recovery from surgery is required (Day 1 of Cycle 4 will be determined by the treating investigator once the subject is cleared to initiate systemic therapy). Nivolumab (480 mg IV infusion on Day 1 of each 4-week cycle) will be administered for up to 9 cycles during the Adjuvant phase.

Follow up:

- All subjects will be followed for 4 weeks after last dose of nivolumab at End of Study (EOS) visit.
- In the absence of disease progression, data from standard of care imaging will be captured every 3 months for 2 years post-surgery and every 6 months thereafter for up to 3 years post-surgery.
- Long-term survival status will be performed every 6 months (by phone) for up to 5 years from study registration, unless the study is terminated early.

Protocol Monitoring Committee (PMC) review: Moffitt PMC will monitor safety and efficacy parameters as specified in the PMC section later in this protocol.

Disclosure Statement: This is a single group treatment study with 1 arm that has no masking.

Number of Subjects: Up to 33 subjects; in Simon minimax Stage 1, up to 22 subjects can be enrolled. If the number of pCR in Stage 1 meet the pre-specified number ($N \geq 3 / 22$), enrollment for Stage 2 will include an additional 11 subjects (for a total of 33 subjects).

Study Duration: For each subject, the total duration of study participation will be 1 year (excluding the Screening period), plus long-term follow-up of up to 5 years (until death, subject withdraws consent or the study was terminated):

- Screening period: up to 4 weeks
- Neoadjuvant phase: 12 weeks (Up to 3 x 4-week cycles)
- Definitive surgery phase: approximately 2-4 weeks

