NOTE: The Investigator/Sub-Investigators are expected to make every reasonable effort to comply with the study calendar and schedule of activities. However, if a cycle is missed or a subject's study treatment and/or testing days need to be rescheduled due to the subject's inability to comply with the study calendar (i.e., COVID-19 related events, hospitalizations, business and vacation travel plans, illness, transportation issues, holidays, family emergencies, etc.), an additional window of \pm one week is available for rescheduling of study treatment and procedures per the discretion of the Sub- Investigator, and as needed discussed with the Investigator.

NOTE: Existing FFPE tumor samples from previous and future (while on study) melanoma tumor biopsies should be requested if available and should be submitted for research purposes. Up to 20 unstained slides may be requested if available. Provision of less than 20 slides is acceptable based on availability. This applies primary melanoma tumor lesions and metastatic melanoma tumor lesions. These should be requested in addition to the protocol indicated research biopsies.

NOTE: Effective July 26, 2023, blood and fecal biospecimens will no longer be collected on study.

Rationale: (1) All patients have completed the neoadjuvant phase of the study; (2) OncoSec is no longer able to support this study or biospecimen collections.

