7.2. Subject Discontinuation/Withdrawal from the Study

Subjects are free to discontinue their participation in the study at any time and without prejudice to further treatment. The Investigator must withdraw any subject from the study if that subject requests to be withdrawn, or if it is determined that continuing in the study would result in a significant safety risk to the subject.

Subjects who discontinue study drug or are withdrawn from the study prior to the first efficacy endpoint will not be replaced.

The subject's participation in the study may be discontinued due to the following reasons:

- Request of Investigator
- Life-threatening event or death
- Subject withdrew consent
- Subject is lost-to-follow-up

The subject may discontinue study medication due to the following reasons:

- Request of Investigator
- AE
- Treatment failure
- Subject is non-compliant with study procedures or study protocol
- Request of regulatory authority
- Pregnancy
- Other (to be specified in the electronic case report form; eCRF)

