9.4. Statistical Analyses

The statistical analysis plan (SAP) will be developed and finalized before database lock and will describe the subject populations to be included in the analyses, and procedures for accounting for missing, unused, and spurious data. This section is a summary of the planned statistical analyses of the primary and secondary endpoints. The SAP may modify the plans outlined in the protocol; however, any major modifications will also be reflected in a protocol amendment.

Since this is an open-label, single arm clinical study, descriptive summary statistics will be employed to analyze the data.

The standard summary statistics for continuous variables are sample size (n), mean, standard deviation, median, minimum and maximum. The standard summary statistics for categorical variables are frequencies and percentages. Time to event variables will be summarized using the Kaplan-Meier method. Where confidence limits are appropriate, the confidence level will be 95% (two-sided), unless otherwise stated. The only test of statistical significance will be performed according to the pre-defined analysis of the Simon 2-stage design.

Individual data (including relevant derived variables) will be presented by parameter in listings. Results of statistical analyses, descriptive summary statistics and supportive listings will also be presented.

Baseline values are defined as the last valid value prior to study drug administration. Baseline safety data will be presented along with subsequent safety values assessed during or after drug administration.

Statistical analyses will be performed using SAS® v9.4 or higher (SAS Institute, Cary NC, USA).

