9.4.3. Efficacy Analyses

Endpoint	Statistical Analysis Methods
Primary	
Primary efficacy analyses will be performed on ASaT Population.
 
The pCR will be estimated based on the proportion of subjects with no viable tumor on histologic assessment at definitive surgery. The estimated pCR will be accompanied by a 2-sided 95% exact binomial confidence interval (CI). Refer to statistical analysis plan (SAP) for detail.

Secondary	
DOR, PFS, iPFS, iBORR and OS (time to events endpoints) will be summarized descriptively using Kaplan-Meier methods. The censoring rules will be defined in the SAP. The ORR, BORR, and iBORR (categorical endpoints) will be summarized in a similar fashion as pCR. These will be assessed by Investigator based on Response Evaluation Criteria In Solid Tumors (RECIST) v1.1 at 12 weeks of Neoadjuvant phase (preoperative, unconfirmed). Refer to SAP for detail. Further, the risk of surgical delay (either due to toxicity and/or tumor progression) will be assessed. Surgery will be planned at about 12 weeks and any delays beyond the protocol allowed window will be monitored and reported.

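### Does the primary analysis need a written success rule in case fewer than 33 subjects are treated?

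*Combined protocol and SAP*

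**What the plan says.** Section 9.2 describes a Simon minimax design against a null pathologic complete response (pCR) rate of 10%, with an alternative of 30%. Accrual stops if Stage 1 gives 2 or fewer responses in 22. Otherwise 11 more subjects are added, and "If 7 or more responses are observed in 33 subjects, the conclusion will be that the therapy is worthy of further investigation". The stated operating characteristics are a type I error of 0.05 and power of 90%.

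Section 9.4 adds: "The only test of statistical significance will be performed according to the pre-defined analysis of the Simon 2-stage design". Otherwise the analysis is descriptive. Section 9.4 also leaves populations and missing data to a separate SAP, to be final before database lock, and promises a protocol amendment for major modifications.

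Section 9.4.3 states: "Primary efficacy analyses will be performed on ASaT Population". Section 9.3 defines that set as enrolled subjects given at least one dose of tavo or nivolumab. The pCR proportion is to be reported with a two-sided exact 95% interval, to which no decision is attached.

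On numbers, the synopsis reads "Up to 33 subjects; in Simon minimax Stage 1, up to 22 subjects can be enrolled", while section 9.2 says that 33 eligible subjects will be enrolled. Section 7.2 reads "Subjects who discontinue study drug or are withdrawn from the study prior to the first efficacy endpoint will not be replaced". The note dated 26 July 2023 at the end of section 1.3 explains why blood and fecal sampling ceased: "All patients have completed the neoadjuvant phase of the study", and "OncoSec is no longer able to support this study or biospecimen collections".

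**The concern.** The single test is tied to exactly 33 subjects, while the analysis set is whoever was dosed. Enrolment is worded as a ceiling, the supporter may end the study at any time (section 10.1.8), and the July 2023 note says that support has ended and neoadjuvant treatment is over. Yet section 9 still reads prospectively and gives no attained number. Someone reading these together would reasonably suspect that accrual fell short.

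If it did, three readings are open: keep 7, recalculate the cut-off for the attained number, or drop the test and rely on the interval. They can disagree. With 6 responses in 25, a fixed bar of 7 is missed; the exact cut-off for 25 is met (type I error 0.033); and the exact 95% interval, 9.4% to 45.1%, includes 10%. The trial is open-label and pCR is read locally, so the choice could be made with the count in hand.

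**Working it through.** **Inputs.** From section 9.2: null rate 0.10, alternative 0.30, Stage 1 of 22 with a stop at 2 or fewer, total 33, success at 7 or more. The attained number N is not in the documents; every value of N below 33 is an assumption.

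**Formula.** For N of 22 or more, with success at r or more and true rate p:

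P(success) = sum over x = 3 to 22 of P[Bin(22, p) = x] × P[Bin(N − 22, p) ≥ r − x].

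For N below 22 it is the single-stage tail P[Bin(N, p) ≥ r].

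**The plan's own figures.** N = 33 and r = 7 give 0.0409 at p = 0.10 and 0.9018 at p = 0.30. A search over two-stage designs with type I error at most 0.05 and power at least 0.90 finds 33 as the smallest total. The stated design reproduces; 0.05 is the ceiling and 0.041 the attained level.

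**Fixed cut-off of 7 against the smallest cut-off with type I error at most 0.05 (N assumed).**

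| N | Type I error / power with 7 | Smallest valid cut-off | Type I error / power with it |
|---|---|---|---|
| 32 | 0.035 / 0.884 | 7 | same |
| 30 | 0.026 / 0.840 | 7 | same |
| 28 | 0.018 / 0.780 | 7 | same |
| 27 | 0.015 / 0.744 | 6 | 0.047 / 0.864 |
| 25 | 0.010 / 0.659 | 6 | 0.033 / 0.807 |
| 22 | 0.004 / 0.506 | 6 | 0.018 / 0.687 |
| 20 | 0.002 / 0.392 | 5 | 0.043 / 0.762 |
| 18 | 0.001 / 0.278 | 5 | 0.028 / 0.667 |

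Over the whole range the smallest valid cut-off is 7 for N = 28 to 33, 6 for N = 21 to 27, and 5 for N = 15 to 20.

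**Where the two rules disagree.** For N = 28 to 32, nowhere. For N = 21 to 27, only at exactly 6 responses; for N = 15 to 20, only at 5 or 6. The chance of landing there is the difference between the two success probabilities. At N = 25 and a true rate of 30%: 0.8065 − 0.6593 = 0.147. At N = 27: 0.8637 − 0.7436 = 0.120.

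**Is the clash with the interval caused by a shortfall?** At the full 33, 7 responses pass the rule, yet the exact 95% interval for 7/33 is 9.0% to 38.9%, which includes 10%. The clash comes from placing a one-sided rule beside a two-sided interval, and it is there at the planned size too.

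**Can N fall below 33?** A subject who is dosed and then stops stays in the analysis set, so the no-replacement clause alone removes nobody. Only under-accrual, or enrolment without dosing, lowers N. The July 2023 note gives no enrolled number; it fits 33 treated, a futility stop at 22, or any other total.

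**The case for a change.** The strongest case for adding text is that the gap is real and cheap to close. No section gives a success rule for fewer than 22 subjects, or for 22 to 32 after 3 or more responses. The sentence deferring detail to the SAP mentions populations and missing data but not an attained-sample-size rule. If N were 25, a bar of 7 would leave 66% power where a valid bar of 6 would give 81%. Shrinking the bar in proportion to 7/33 would be worse: 6 or more at N = 28 has a type I error of 0.055, and 5 or more at N = 23 has 0.073. One might also worry that 3 responses in an unfinished Stage 1 could be presented as success; under the 10% null that happens with probability 0.27 at N = 18 and 0.38 at N = 22.

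The arithmetic stands, and so does the absence of a written contingency. The rest is weaker. The planned early stop at 2 or fewer in 22 is covered. Every mention of 3 responses makes it a condition for opening Stage 2, so the success reading has no footing in the text. The loss of power matters only if a shortfall occurred, which no document shows. And if the pCR count is already known, which is plausible in an open-label trial whose neoadjuvant phase has finished, a cut-off written now could not be called pre-specified. The defensible report would then be the proportion with its interval, which section 9.4.3 already specifies.

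**Conclusion.** No change is needed. A contingency is left unwritten, and analysts following the plan would handle it soundly. If 33 subjects were dosed, section 9.2 applies as it stands. If fewer were dosed, holding to 7 keeps type I error at or below 0.041, and a trial that reaches 7 early would have met the 33-subject bar whatever the remaining subjects showed. The exact interval is valid at any N as an estimate.

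The cost of the silence is bounded: lower power if 7 is retained, and an unsettled reading of exactly 6 responses at N = 21 to 27 or of 5 to 6 at N = 15 to 20. For one to five missing subjects, a recalculated cut-off would change nothing.

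This rests on three assumptions: the attained N, which is not given; that any shortfall arose for reasons unrelated to pCR; and that the SAP named in section 9.4, which is not among the documents, does not contradict section 9.2. Reporting N and the reason accrual ended is ordinary good practice and needs no amendment.

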9.3. Populations for Analyses

For purposes of analysis, the following populations are defined:

Population	Description
All Subjects as Treated (ASaT) / Safety	All enrolled subjects who received at least 1 dose of either study intervention (tavo or nivolumab)

9.4. Statistical Analyses

The statistical analysis plan (SAP) will be developed and finalized before database lock and will describe the subject populations to be included in the analyses, and procedures for accounting for missing, unused, and spurious data. This section is a summary of the planned statistical analyses of the primary and secondary endpoints. The SAP may modify the plans outlined in the protocol; however, any major modifications will also be reflected in a protocol amendment.

Since this is an open-label, single arm clinical study, descriptive summary statistics will be employed to analyze the data.

The standard summary statistics for continuous variables are sample size (n), mean, standard deviation, median, minimum and maximum. The standard summary statistics for categorical variables are frequencies and percentages. Time to event variables will be summarized using the Kaplan-Meier method. Where confidence limits are appropriate, the confidence level will be 95% (two-sided), unless otherwise stated. The only test of statistical significance will be performed according to the pre-defined analysis of the Simon 2-stage design.

Individual data (including relevant derived variables) will be presented by parameter in listings. Results of statistical analyses, descriptive summary statistics and supportive listings will also be presented.

Baseline values are defined as the last valid value prior to study drug administration. Baseline safety data will be presented along with subsequent safety values assessed during or after drug administration.

Statistical analyses will be performed using SAS® v9.4 or higher (SAS Institute, Cary NC, USA).

9.4.1. Subject Disposition

A detailed description of subject disposition will be provided. It will include:

- The number of subjects who were included in the safety analysis sets
- A summary of subjects who complete the protocol
- A summary of reasons for subject discontinuation
- A summary of reasons for subject with treatment failure
- An account of all identified protocol violations

All subject enrolled in the study will be accounted for in the summation.

9.4.2. Demographic and Baseline Characteristics

Demographic characteristics including age, gender, race, and ethnicity will be presented in the form of tabular summary statistics for all ASaT analysis set. Other subject baseline characteristics including weight, height, body mass index (BMI), initial stage of disease, and performance status will be presented similarly.

9.4.3. Efficacy Analyses

Endpoint	Statistical Analysis Methods
Primary	
Primary efficacy analyses will be performed on ASaT Population.
 
The pCR will be estimated based on the proportion of subjects with no viable tumor on histologic assessment at definitive surgery. The estimated pCR will be accompanied by a 2-sided 95% exact binomial confidence interval (CI). Refer to statistical analysis plan (SAP) for detail.

Secondary	
DOR, PFS, iPFS, iBORR and OS (time to events endpoints) will be summarized descriptively using Kaplan-Meier methods. The censoring rules will be defined in the SAP. The ORR, BORR, and iBORR (categorical endpoints) will be summarized in a similar fashion as pCR. These will be assessed by Investigator based on Response Evaluation Criteria In Solid Tumors (RECIST) v1.1 at 12 weeks of Neoadjuvant phase (preoperative, unconfirmed). Refer to SAP for detail. Further, the risk of surgical delay (either due to toxicity and/or tumor progression) will be assessed. Surgery will be planned at about 12 weeks and any delays beyond the protocol allowed window will be monitored and reported.

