9.5. Interim Analyses

No formal interim analyses are planned for this study. Because a Simon 2-stage minimax design will be employed, response rate data will be assessed at Stage 1 to determine whether enrollment should proceed to Stage 2 per the defined stopping rules.

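### Does it matter that at exactly 7/33, the lowest passing count, the planned 95% interval for pCR still contains the 10% null?

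*Combined protocol and SAP*

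**What the plan says.** Section 9.1 sets the hypotheses: "It is anticipated that combination regimen will improve the pCR from an estimated 10% to 30" per cent. Section 9.2 chooses a Simon minimax design with 22 subjects in stage 1, continuation at 3 or more responses, and 11 further subjects. The final rule is: "If 7 or more responses are observed in 33 subjects, the conclusion will be that the therapy is worthy of further investigation". The section adds that "this design yields a Type I error rate of 0.05 and power of 90" per cent. It does not say whether the 0.05 is one-sided.

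Section 9.4.3 attaches an interval to the primary estimate: "The estimated pCR will be accompanied by a 2-sided 95% exact binomial confidence interval (CI"). It leaves further detail to a SAP that Section 9.4 says will be finalised before database lock. The level matches the general default in Section 9.4: "Where confidence limits are appropriate, the confidence level will be 95% (two-sided), unless otherwise stated".

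Section 9.4 also separates testing from description. The study is open-label and single-arm, so the data are summarised descriptively, and "The only test of statistical significance will be performed according to the pre-defined analysis of the Simon 2-stage design". Section 9.5 limits the stage 1 look to the same rule: "response rate data will be assessed at Stage 1 to determine whether enrollment should proceed to Stage 2 per the defined stopping rules".

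**The concern.** A reader normally expects the interval beside a primary result to tell the same story as the test. Here the test spends up to 5% in one tail and the interval 2.5% in that tail, so some outcome can pass the test while the interval still covers the null. That outcome is the go boundary itself.

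At 7/33 the report would state that the regimen merits further study next to a lower limit below 10%. If someone took the interval as the test, success would in effect require 8/33, and the design would lose power without anyone having decided so. The protocol has no sentence in Section 9.4.3 on how to read the two side by side, and the text supplied plans no interval at the rule's own level.

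**Working it through.** **Inputs.** p0 = 0.10 and p1 = 0.30 (Section 9.1). n1 = 22, stop at 2 or fewer, n = 33, pass at 7 or more (Section 9.2). Two-sided 95% exact interval (Section 9.4.3), taken as Clopper-Pearson. The denominator is assumed to be 33, meaning all 33 subjects were dosed and are in the ASaT set.

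**1. Reproduce the design.** The probability of a final count T of at least s is

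P(T ≥ s | p) = Σ over x = 3..22 of Bin(x; 22, p) × P(Bin(11, p) ≥ s − x).

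- At p = 0.10, P(T ≥ 7) = 0.0409.
- At p = 0.30, P(T ≥ 7) = 0.9018.

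This agrees with the stated 0.05 (as a ceiling) and 90%. A search over designs returns 22/33 with these boundaries as the minimax choice. The rule rejects only for high counts, so the 0.05 is one-sided by construction.

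**2. Planned interval near the boundary.** For x of 33, the lower limit is the 0.025 quantile of Beta(x, 34 − x) and the upper limit is the 0.975 quantile of Beta(x + 1, 33 − x).

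| Count | Rule | 95% exact interval | Contains 10%? |
|---|---|---|---|
| 6/33 | fail | 6.98% to 35.46% | yes |
| 7/33 | pass | 8.98% to 38.91% | yes |
| 8/33 | pass | 11.09% to 42.26% | no |

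Only 7/33 differs.

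**3. How often.** P(T = 7) = P(T ≥ 7) − P(T ≥ 8).

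- At 10%: 0.0409 − 0.0140 ≈ 0.027.
- At 30%: 0.9018 − 0.8165 = 0.0853.

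At a true rate of 20%, which the design does not use, it would be 16.1%.

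**4. What misreading the interval as the test would cost.** Requiring 8/33 would lower power from 0.9018 to 0.8165 and type I error from 0.0409 to 0.0140. The plan does not do this, because the count decides.

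**5. Cause.** Inverting the two-stage tail probability at 2.5% per tail gives 9.02% to 38.97% at 7/33, which still contains 10%. So the two-stage sampling is not the reason; the level is. At 5% per tail the two-stage interval at 7/33 is 10.45% to 36.23%, and the ordinary exact 90% interval is 10.40% to 36.18%. Both exclude 10%.

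**6. Is the planned interval valid under two-stage sampling?** I enumerated all outcomes, including early stops at 0 to 2 of 22, over true rates from 2% to 70%. Overall coverage of the planned 95% interval never falls below 95.0%. Its upper limit falls below the true rate at most about 3.4% of the time, against a nominal 2.5%, near a true rate of 29%. The lower tail is conservative enough to keep total coverage at or above nominal.

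**The case for a change.** The strongest case for a change is that it would be cheap and the awkward outcome is not remote. Section 9.4 says what is tested, but it does not tell a reader of the report what to make of an interval that covers the null beside a pass. Two or three sentences could state that the 0.05 is one-sided, add a two-stage exact 90% interval whose lower limit matches the rule (8.4% to 33.0% at 6/33, 10.5% to 36.2% at 7/33) with its p-value (0.100 and 0.041), and label the 95% interval descriptive.

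The arithmetic stands. The need does not follow from it.

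- Section 9.2 ties the conclusion to the count, and Section 9.4 makes that count the only test. A sentence saying the rule governs would repeat what is there, and one-sidedness is plain from the form of the rule.
- Sections 9.4 and 9.4.3 agree with each other on two-sided 95%. Nothing in the plan promises that the interval is the inverse of the test. A conventional 95% interval for estimation beside a one-sided 5% screening rule is a fair choice of reporting level.
- At 7/33 the extra p-value repeats the attained error rate of the rule, and the alternative point estimate that allows for the two stages moves 21.2% only to 21.6%.
- A note to the schedule of activities in Section 1.3, effective July 26, 2023, says that all patients have completed the neoadjuvant phase. In an open-label trial, a narrower interval added after that point, at a level that makes the boundary result exclude 10%, could look chosen after the fact.

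Saying that no interval at the rule's level is planned also goes only as far as the protocol text, since detail is left to a SAP not supplied here.

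**Conclusion.** No change to the plan follows. The mismatch is real but confined to one count, 7/33, with probability 8.5% at the design alternative and 2.7% at the null. It arises from pairing a one-sided 5% rule with a two-sided 95% interval. The go decision, the attained type I error of 4.1%, the power of 90.2% and the coverage of the interval are all unaffected. The protocol already makes the count rule decisive and the interval descriptive.

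An analyst who meets 7/33 can report the pass under the Simon rule, give the 95% interval as an estimate of precision, and note the difference in level. That sentence fits in the SAP or the report at the authors' discretion; a 90% interval, a p-value or an adjusted estimate would be a matter of preference.

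This rests on an analysed denominator of 33 and on reading the exact binomial interval as Clopper-Pearson. Section 1.1 allows up to 33 subjects, so with another final number the boundary figures would have to be recalculated.
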